## METHODS

A sample size of 30 patients with ESRD5D (ages 21-70 years) will be utilized for this study. The thirty subjects will be randomized to intervention or active control; 15 per group. We anticipate a 20% drop out rate and an additional 10% screen failure rate. Therefore, we anticipate consenting a total of 40 subjects. Subjects will be recruited through Nebraska Medicine Nephrology clinics.

Subjects will be consented and screened in the Diabetes Center at UNMC. All candidates for the study will be adults (aged 21-70 years) on maintenance hemodialysis at any UNMC directed dialysis unit. Other inclusion criteria include 1) a timed up and go score of > 13.5 seconds; 2) ambulatory, without a walking aid (i.e., cane or walker); 3) able to complete the various questionnaires interactively with the research nurse; 4) venous access that can be accomplished without unusual difficulty; and 5) greater than 3 months on hemodialysis. Subjects will be excluded if they are 1) pregnant; 2) on peritoneal dialysis; 3) allergic to vitamin D; 4) have diagnosed liver disease; and/or 5) an intestinal disorder that would interfere with vitamin D absorption. They will also be excluded if they are currently taking vitamin D supplements >800 IU per day, glucocorticoids, anticonvulsants, or other drug therapies for osteoporosis.

At the baseline visit, the subject will be screened for eligibility by a physical exam, including vital signs, height, weight, and a detailed history, including medical history, medications, personal fracture & fall history, menstrual history, diabetic history, sun exposure history, and alcohol and tobacco use. Vital signs, height, and weight will be recorded. A validated Food Frequency Questionnaire will be completed to assess dietary vitamin D intake. Previous records of health history and fracture documentation will be requested. Each subject will undergo phlebotomy of 13ml.

Subjects will be randomized into one of two groups. Each subject will take a daily, oral capsule containing vitamin D (4000 IU) for 3 months or active control (800 IU vitamin D). We chose to use a daily dose, as it has been proposed that a steady state of vitamin D levels provides a constant source of substrate for enzymes converting it to 25(OH)D. This dose will increase serum 25(OH)D levels to ~60 ng/ml by 12 weeks. The active control will be 800 IU of vitamin D consistent with the recommendations developed by the Food and Nutrition Board of the Institute of Medicine.

Subjects will then travel to the Biomechanics Research Building at the University of Nebraska at Omaha. Subjects will then be asked to undergo static and dynamic balance tests, the timed up and go (TUG), the Fullerton Advanced Balance scale (FAB), and gait speed over 20 meters (see Functional test descriptions below). They will also undergo muscle strength and endurance testing of the quadriceps and hamstrings of both limbs. The subject will be issued a pill bottle containing a 3-month supply of the interventional drug (see below). A fall diary will be given to the subject as well.

At 3 months of the study, the subject will be interviewed for changes to medical history & sun exposure. Height and weight will be recorded. Subjects be asked to undergo the same physical function tests as baseline. Each subject will undergo phlebotomy of 13ml. Pill bottles will be collected for a pill count.

*Functional test descriptions:*

Static and Dynamic Balance: will be measured through the Neurocom Balance Manager System. The two laboratory tests that will be used are the Sensory Organization Test (SOT) and the Motor Control Test (MCT). The purpose of the SOT is to assess the three sensory systems that encompass balance. There are six conditions (combinations of manipulating vision,

proprioception, and the vestibular system) with 3-20 second trials for each. The SOT provides an equilibrium score that is ranked on a 0-100% scale, where 0% = reaching the point of falling or has fallen and 100% = no movement of the body while standing. The purpose of the MCT is to examine the body's automatic response to correction of posture to a moving surface. There are three trials and six conditions in which the base that the subject stands on is perturbed slightly (moved forward or backward). The MCT scores for latency, the time it takes in milliseconds (msec) for an individual's center of gravity to respond to the movement. A longer latency would indicate that it takes longer for the nervous system to respond to the movement.

Timed Up and Go (TUG): The subject is observed while rising from a chair, walking 3 meters, and returning to the chair. A score >12 seconds is indicative of fall risk.

Fullerton Advanced Balance scale (FAB): is a series of balance tests to assess the subject's ability to use his/her somatosensory cues to maintain upright balance in varying situations. There are ten tasks in the scale and they are scored on a range from zero to four. Zero being unable to complete the task and four being able to complete the task independently with no assistance. Scoring less than 25/40 is considered to be at risk for falling.

20-meter Gait Speed: provides a marker of health status and survival. The subject will be instructed to walk 20 meters at his/her preferred walking speed. Time is measured while the individual walks the set distance.

Muscle Strength and Endurance: Quadriceps and hamstring muscle strength and endurance will be assessed using an isokinetic dynamometer (Biodex System 4, Biodex Medical Systems, Inc., Shirley, NY). Both limbs will be assessed. Standard testing protocols will be used. This testing will be done at the end of the visit as other measures could be affected by the fatigue induced by this testing.

Dependent variables will be checked for normality. Non-parametric tests will be utilized where appropriate. For each outcome, linear mixed-effects models (LMM) will be conducted. The model will include one of the dependent variables as the outcome variable and treatment group and time as independent variables as well as their interaction. The LMMs will also be adjusted for possible covariates (e.g., age, medication history, sun exposure). Significance will be determined at an alpha < 0.05 level.

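### No serum calcium criterion at entry: a subject whose calcium is already above normal can be randomised to 4000 IU/day of vitamin D for 3 months

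*Combined protocol and SAP*

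**What the plan says.** All references are to METHODS in the combined protocol and SAP.

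- **Inclusion.** Subjects are adults aged 21 to 70 on maintenance hemodialysis who meet five numbered items, the first introduced as "Other inclusion criteria include 1) a timed up and go score of > 13.5 seconds". The other four cover walking without an aid, completing questionnaires, venous access and time on dialysis.
- **Exclusion.** There are five numbered conditions (pregnancy, peritoneal dialysis, vitamin D allergy, liver disease, and intestinal disease affecting absorption) and four current-drug exclusions. The drug exclusions begin "They will also be excluded if they are currently taking vitamin D supplements >800 IU per day" and go on to glucocorticoids, anticonvulsants and osteoporosis drugs.
- **Screening.** "At the baseline visit, the subject will be screened for eligibility by a physical exam, including vital signs, height, weight, and a detailed history". Earlier health records are also requested.
- **Blood.** "Each subject will undergo phlebotomy of 13ml" appears at baseline and again at 3 months. In neither place is a result tied to eligibility.
- **Treatment.** Subjects are randomised to 4000 IU or 800 IU daily for 3 months. The plan expects the higher dose to bring 25(OH)D to about 60 ng/ml by 12 weeks. On dispensing: "The subject will be issued a pill bottle containing a 3-month supply of the interventional drug (see below".

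**The concern.** The plan already treats vitamin D exposure as relevant to entry, since it caps current supplements. That cap limits an intake. It does not identify a subject whose calcium is raised for any reason. The trial then gives half its subjects a substantially higher dose of an agent that can raise calcium further. That last premise is general pharmacology and is not stated in the documents.

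What is at stake is the safety of individual subjects, not the validity of the comparison. If raised calcium does not bar entry, whether such a subject is dosed depends on an investigator happening to notice it.

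**Working it through.** The plan states no figure on this point, so the check is a reading of each criterion, followed by simple dose arithmetic.

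**Step 1. Would any listed item stop a subject with raised calcium?**

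| Group of criteria | Items | Refers to calcium or another laboratory value? |
|---|---|---|
| Age and maintenance hemodialysis | 2 | No |
| Numbered inclusion items | 5 | No: function, mobility, questionnaires, venous access, dialysis duration |
| Numbered exclusion conditions | 5 | No |
| Current-drug exclusions | 4 | No: they restrict what is taken, whatever the calcium value |

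Items examined: 2 + 5 + 5 + 4 = 16. Items that set a calcium limit: 0. The liver and intestinal exclusions and the supplement cap do not act as a calcium limit by another route.

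**Step 2. Does the visit sequence supply the check?** Blood is drawn at baseline, before randomisation is described. No criterion uses the result, and randomisation and issue of the bottle are not made to wait for it. The next draw described is at 3 months, when the supply has been used.

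**Step 3. What could such a subject receive?** Inputs: 4000 and 800 IU/day from METHODS, with 3 months taken as 91 days.

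- Ratio: 4000 / 800 = 5.
- Higher dose: 4000 × 91 = 364,000 IU.
- Control: 800 × 91 = 72,800 IU.
- Difference: 364,000 − 72,800 = 291,200 IU.
- A subject who enters on a permitted 800 IU/day supplement and continues it would take 4000 + 800 = 4800 IU/day in the higher-dose group. The text available does not say whether the supplement stops.

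These figures describe exposure only. They say nothing about what calcium would do.

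**Step 4. How many subjects?** This would need the share of otherwise eligible patients with calcium above the limit. The documents give neither that share nor any calcium data, so no count is offered.

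**The case against.** The best case for the plan has four parts.

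1. *The text available is partial.* The dispensing sentence points to a drug description that does not appear in it, and laboratory or safety sections may exist elsewhere. This stands against any claim about analytes or monitoring. It does not reach the eligibility list, which runs without a visible gap and is where a calcium exclusion would belong.
2. *The screening sentence is a summary.* It omits the timed up and go test, although that test is an inclusion item, so it cannot be read as the full set of checks. This is correct, but the point rests on the list of criteria and not on that sentence.
3. *Investigators have other routes.* Medical history, medications and earlier records are collected, and a recent calcium value may be in them. This also stands, and it makes the fix cheaper. It does not turn raised calcium into a reason for exclusion.
4. *The lead-in to the inclusion items could signal an open list.* The exclusions carry no such wording.

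Two stronger readings are tempting. A reader might infer that the trial has no calcium monitoring or stopping rule. None appears in the text available, but because that text is partial, its silence does not show the plan lacks one. A reader might also infer that baseline 25(OH)D should cap entry or must enter the model. The covariate sentence is open-ended: "The LMMs will also be adjusted for possible covariates (e.g., age, medication history, sun exposure". Baseline 25(OH)D is therefore not ruled out, and nothing in the documents shows that the treatment effect depends on it.

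**Conclusion.** The point holds for the entry rule. As written, raised calcium does not prevent randomisation to 4000 IU/day or issue of a 3-month supply. The conclusion rests on the eligibility list being complete as printed and on the general premise that vitamin D can raise calcium.

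The dose contrast is known (fivefold), but the number of subjects affected is not and may be zero. A reader might infer that an appreciable part of the 15-subject higher-dose group would be hypercalcaemic, or that harm is likely. The documents support neither inference, and any percentage would only restate an assumed prevalence.

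This is a cheap improvement for patient safety. It is not a flaw that undermines the trial's comparison.

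**What to change.** Add one exclusion to the eligibility paragraph: *serum calcium above the upper reference limit of the reporting laboratory*. Require the investigator to see the value before randomisation and before the bottle is released. Use a recent result from the subject's records where one is available, with the sponsor stating how recent it must be. Otherwise use the baseline 13 ml draw. Because the exclusion is applied before randomisation, it leaves the analysis unchanged.

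Costs:

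- **Assay.** One calcium check for subjects without a usable recent value. The documents do not say how the 13 ml is allocated, so the sponsor should confirm that volume and tubes are suitable.
- **Timing.** Dispensing may be delayed for those subjects. The baseline function tests can still go ahead the same day, though anyone then excluded will have done them unnecessarily. Handing over the bottle at the subject's own dialysis unit could avoid an extra trip.
- **Recruitment.** Perhaps a few more screen failures. The plan's allowance is "We anticipate a 20% drop out rate and an additional 10% screen failure rate"; read as a share of the 40 to be consented, 10% is 40 × 0.10 = 4 subjects. Whether calcium exclusions would fit within those 4 cannot be judged from the documents, so the sponsor should track them and consent more subjects if needed.

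### Cheap improvement, not an error: the group by time test leaves the equal baseline means unused, and adjusting for the outcome's own baseline gains precision unless that analysis is overloaded with covariates

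*Combined protocol and SAP*

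**What the plan says.** All of this is in METHODS of the combined protocol and SAP.

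- **Visits.** Function is tested at baseline and once more, at 3 months: "Subjects be asked to undergo the same physical function tests as baseline".
- **Model.** For each outcome a linear mixed model has "treatment group and time as independent variables as well as their interaction". Baseline is therefore one of the two responses, and the arms' baseline means are left free to differ. The text does not say which coefficient is the treatment effect; the interaction is the natural reading.
- **Covariates.** "The LMMs will also be adjusted for possible covariates (e.g., age, medication history, sun exposure" introduces examples only. The outcome's own baseline value is not among them.
- **Non-parametric branch.** "Dependent variables will be checked for normality. Non-parametric tests will be utilized where appropriate".
- **Size.** "The thirty subjects will be randomized to intervention or active control; 15 per group". Also "We anticipate a 20% drop out rate and an additional 10% screen failure rate", and "Therefore, we anticipate consenting a total of 40 subjects".
- **Entry rule.** Patients need "a timed up and go score of > 13.5 seconds".

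No effect size, SD, correlation or power is stated.

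**The concern.** With only two measurements per patient, the interaction compares mean changes. A change score subtracts the whole baseline value, whatever its correlation with the 3-month value. Randomisation makes the expected baseline means equal, so the analysis may subtract only the share of baseline that predicts the 3-month value. Unless r is close to 1, that gives a smaller variance for the same treatment effect. With 15 patients per arm, and perhaps 12 with 3-month data, the precision lost could matter, and the baseline values are already being collected.

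**Working it through.** **Inputs from METHODS.** 15 per arm; 20% drop-out; alpha 0.05 (taken as two-sided); one baseline and one 3-month function test.

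**Assumed, because the documents are silent.** Effect 0.8 SD (0.5 SD also shown); r from 0.5 to 0.95; equal SD s at both visits; normal outcomes.

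**The plan's own numbers.** The 30 cannot be reproduced without an effect size, SD and power. The 40 can, roughly: 30/(0.8 × 0.9) = 41.7, and 30 × 1.3 = 39. In the other direction 40 × 0.9 × 0.8 = 28.8, so 30 may be the intended evaluable number, although the text says thirty are randomised. Both readings are covered below.

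**Step 1: what the planned term estimates.** With complete pairs and covariates fixed over time, the interaction equals the difference in mean change. In one simulated data set with an age covariate, the mixed model and the change-score comparison both gave 0.843 with SE 0.257.

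**Step 2: variances without other covariates.** With N patients in total:

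- Change: 2s²(1−r), N−2 df.
- ANCOVA on baseline: s²(1−r²) × (N−3)/(N−4), N−3 df. The last factor is the cost of estimating the slope; at N=30 it is 27/26.
- Ratio, ANCOVA to change: (1+r)/2 × 27/26.

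Example at r=0.5, n=15 per arm. Change: SE = √(2 × 1.00/15) = 0.365, and 0.8/0.365 = 2.19. ANCOVA: 0.75 × 27/26 = 0.779, SE = √(2 × 0.779/15) = 0.322, and 0.8/0.322 = 2.48. Power follows from the noncentral t.

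| r | Variance ratio | Planned | ANCOVA on baseline | Gain (points) |
|---|---|---|---|---|
| 0.5 | 0.78 | 56.2% | 66.8% | 10.6 |
| 0.7 | 0.88 | 77.9% | 82.7% | 4.7 (unrounded) |
| 0.9 | 0.99 | 99.7% | 99.7% | 0.0 |

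A 20,000-trial simulation agreed: 55.6 v 66.5%, 78.2 v 83.0% and 99.7 v 99.8%. At 0.5 SD the gains are 5.9 points (r=0.5) and 4.2 points (r=0.7).

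**Step 3: drop-out.** With 3 of 15 per arm lacking 3-month data and 0.8 SD, the planned mixed model v completer ANCOVA (60,000 simulated trials per case) gave 48.8 v 56.2% at r=0.5, 69.6 v 72.2% at r=0.7 and 84.7 v 85.6% at r=0.8. The gains are about 7, 3 and 1 points.

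**Step 4: the entry rule.** Restricting TUG shrinks the baseline variance Vx (unrestricted SD = 1). The change variance becomes (1−r)²Vx + (1−r²), while ANCOVA keeps (1−r²), so the gap narrows. With an assumed TUG mean of 12–15 s and SD of 4 s, 15 per arm and 0.8 SD, the gains in points are:

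| Outcome | r=0.5 | r=0.7 | r=0.8 |
|---|---|---|---|
| TUG | 2–4 | 0–1 | about 0 |
| Correlated 0.7–0.8 with TUG | 6–8 | 2–3 | under 1 |

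**Step 5: the plan's covariates.** Time-fixed covariates do not alter the planned interaction estimate with complete pairs. In a 3-month ANCOVA each one costs a degree of freedom and some variance. With baseline plus three non-prognostic covariates (an assumed number) the factor is (N−3)/(N−7), or 27/23 at N=30. The variances then break even where (1+r)/2 × 27/23 = 1, that is r = 46/27 − 1 = 0.70. Simulated power at 0.8 SD, planned v ANCOVA with baseline and all three:

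| r | 15 per arm | 12 completers per arm |
|---|---|---|
| 0.5 | 57 v 62% | 47 v 49% |
| 0.7 | 78 v 78% | 66 v 64% |
| 0.8 | 92 v 90% | 85 v 80% |

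A mixed model with a common baseline mean and the covariates as main effects keeps the gain. Its variance was 0.80, 0.90, 0.98 and 1.00 of the planned test's at r = 0.5, 0.7, 0.8 and 0.9 (15 per arm).

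**Step 6: very high r.** At r=0.95, baseline-only ANCOVA has a variance ratio of 0.975 × 27/26 = 1.012 with 15 pairs per arm and 0.975 × 21/20 = 1.024 with 12.

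**The case against.** The strongest objection concerns the covariates. The plan's model contains them, so a comparison without any is not a comparison with the plan as written. They cost the planned interaction essentially nothing, but they cost a 3-month ANCOVA precision. This stands. Step 5 shows a sponsor who moved the whole list into an ANCOVA could do worse than the plan. A reader might infer from Step 2 that baseline adjustment is always free, or costs one degree of freedom whatever else is in the model. That holds only for ANCOVA on baseline alone. It does not defeat the point, because the common-baseline mixed model retains the gain with the covariates in place.

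The size of the gain also rests on figures that the documents do not give. That stands too. At r=0.5, 11 points is near the top of the range over effect sizes: it is about 6 at 0.5 SD and again at 1.2 SD.

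The covariate list is open-ended, so the baseline value might be meant to join it. Nothing commits to that. As a main effect in a model where baseline is already a response, it would leave the interaction estimate unchanged with complete pairs.

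Finally, the TUG entry rule might be thought to favour adjustment by lowering r. It also narrows the baseline, and the net effect is a smaller gain (Step 4).

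**Conclusion.** The point holds as an efficiency improvement. A reader might go further and call the planned model invalid or biased; the documents do not support that, because the difference in mean change is a valid comparison of randomised arms.

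Under the stated assumptions the gain is about 11 points at r=0.5, 5 at r=0.7 and none at r=0.9, with 15 complete pairs per arm, 0.8 SD and no other covariates. It is about 6 and 4 points at 0.5 SD, and about 7 and 3 with 3 of 15 per arm missing at 0.8 SD (r=0.5 and 0.7 in each case). It is smaller again for TUG and outcomes correlated with it. The direction is secure for low to moderate r; the size is not, since r and the effect size are assumed. The conclusion covers function tests analysed by the parametric model. It does not extend to the non-parametric branch, where the trade-off is different, or to falls recorded in the diary.

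**What to change.** For each function test analysed parametrically, state that the treatment effect is the between-arm difference at 3 months, and name one of two routes in advance:

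1. A mixed model on both visits with a common baseline mean across arms, an unstructured 2×2 covariance and the plan's covariates as main effects. Do not also enter baseline as a covariate. Name a small-sample correction such as Kenward-Roger: without covariates, uncorrected standard errors with a normal critical value gave type I error of 7.0–7.3% (15 per arm) and 7.4–7.8% (12 completers).
2. ANCOVA of the 3-month value on that outcome's baseline alone, or with at most one or two covariates named in advance as prognostic. Do not add the full covariate list.

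Without other covariates, and with only 3-month values missing, the two routes give the same estimate. With three covariates they differed by 0.08 SD on average with complete data and by 0.14 SD with 3 of 15 per arm missing, so the choice must be fixed beforehand.

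The cost is analysis-plan wording; no new data are needed. Near r=0.9 or above there is nothing to gain, and baseline-only ANCOVA may lose up to about 2–3% in variance.
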